3.4.2.3 Subject death

Personnel at the investigational site should notify BIOTRONIK as soon as possible concerning any subject death during the investigation. This notification should include a completed study termination eCRF, death certificate, and a copy of the notification of the death sent to the IRB. If a death certificate is not available, a detailed statement (death report) signed by the investigator should be written in addition to the termination eCRF. The death report should include all of the following, if available:

- date and time of death
- place death occurred
- identification of the rhythm at the time of death, if known (include any available documentation)
- immediate cause of death
- any other circumstances surrounding the death
- whether it was device or procedure related

All implanted devices that are involved with the investigational study should be removed and returned to BIOTRONIK.

All deaths occurring while enrolled in the MPP study will be reviewed by the CEC.

3.4.2.4 Sentus QP lead or BIOTRONIK CRT-D extraction

If prior to MPP enrollment, any subject who has the BIOTRONIK Ilivia 7 HF-T QP family CRT-D system or Acticor/Rivacor HF-T QP family CRT-D system and/or Sentus QP LV lead explanted and not replaced with an MPP sub-study eligible system will be withdrawn from the clinical investigation. After documentation of the system revision procedure (Section 3.3.8.3), a Study Termination eCRF should be completed.

Whenever possible, devices that are explanted must be returned to BIOTRONIK, Inc. for analysis.

3.4.2.5 Lost to follow-up

Subjects lost to follow-up are those for whom contact is lost despite the investigator's best efforts to locate the subject. Study sites should attempt to contact these subjects in order to maintain study visit compliance and all contact

attempts should be documented. At a minimum, the site should make two attempts to contact the subject by phone and one attempt by certified mail.

In the event the subject cannot be contacted using the above methods, the subject is terminated from the clinical investigation by completing a Study Termination eCRF.

3.4.2.6 MPP Sub-Study Completion

Subjects who complete the MPP 6 month follow-up visit will be exited with reason of MPP sub-study completion selected on the Study Termination eCRF; however a QP ExCELS Study Termination eCRF is not required.

3.4.3 Date of Study Termination

The expected study termination for all subjects should not be earlier than the 6 month follow-up visit.

For all early study terminations, the following rules apply:

- In case of withdrawal of consent, date of study termination is the date of withdrawal of consent.
- In case of subject death, the date of study termination is the date of death.
- If subject is lost to follow-up, date of termination is the date of last documented contact with the subject.
- If BIOTRONIK Ilivia 7 HF-T QP family CRT-D system or Acticor/Rivacor HF-T QP family CRT-D system and/or Sentus QP LV lead was not implanted, the date of termination is the date of decision not to implant.
- If prior to MPP enrollment, the BIOTRONIK Ilivia 7 HF-T QP family CRT-D system or Acticor/Rivacor HF-T QP family CRT-D system and/or Sentus QP LV lead was explanted and not replaced with an MPP sub-study eligible system, the date of study termination is the date of system revision.

Study related procedures and documentation should end at the day of study termination for the respective subject.

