2.5 Adjustments to Overall Sample Size

Due to the inclusion of interim analyses, a total of 90 evaluable subjects are required to demonstrate superiority to a performance goal of 3%. Assuming a 10% loss to follow-up rate during the study for reasons unrelated to the study outcomes, a total enrollment of 100 subjects would be required to achieve an evaluable study population of 90 subjects.

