2.6.1 Replacement of Missing Data

The last observation carried forward (LOCF) principle will be utilized for the analysis of NYHA Classification and Patient Global Assessment for primary endpoint 1 and secondary endpoints 2 and 3.

Missing NYHA and patient global assessment data at either the enrollment or follow-up visits affects the number of subjects that can be included in the analysis. It is possible that subjects or study personnel may either forget or choose not to answer one or more of the questions related to NYHA classification or patient global assessment.

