2.6.2 MPP Sub-Study Analysis Population

The primary and secondary endpoint analyses will be conducted according to the intention-to-treat principle (ITT) utilizing all available data from fully enrolled subjects. Subjects are expected to remain programmed with the MPP feature ON from MPP enrollment through the completion of the sub-study. Subjects who have the MPP feature permanently turned OFF prior to completion of the sub-study will be required to report a protocol violation; however, these subjects will be included in the analysis population. All available data from subjects that undergo a pulse generator change and no longer have an MPP eligible device will be included in the analysis. Subjects may have the MPP feature temporarily turned OFF due to a lead revision procedure and these short durations with MPP will not be reported as a protocol violation.

Any QP ExCELS subject that does not enroll into the MPP sub-study but receives MPP due to the physician's determination will not be analyzed towards the MPP study endpoints.

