5.1.1 Clinical Events Committee – MPP Sub-Study Events

The QP ExCELS Clinical Events Committee (CEC) described in Section 5.1 will adjudicate all adverse events that require additional invasive intervention to resolve which may be related to the MPP feature. These events include any software issues related to MPP programming or any adverse event that occurs while MPP is enabled and that may be attributed to the use of the MPP feature. The CEC will indicate whether the adverse event is related, possibly related, not related, or has an unknown relation to the MPP feature.

In addition, the CEC will adjudicate all deaths reported while participating in the MPP sub-study and classify each death as cardiovascular, vascular, non-cardiovascular/vascular, or unknown.

The CEC will adjudicate all reported protocol-defined hospitalizations while a subject is enrolled in the MPP sub-study. Hospitalization events will be classified as cardiovascular, vascular, non-cardiovascular/vascular, or unknown. Additionally, hospitalizations classified as cardiovascular will be further classified as a HF hospitalization, non-HF hospitalization, or unknown. Hospitalization events reported by the investigator as part of the initial responder classification for enrollment into the MPP sub-study will not be adjudicated by the CEC.

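### For MPP subjects lost to follow-up, a non-fatal HF hospitalization discovered after the last contact is left outside collection and adjudication, while carried-forward NYHA can still score a responder

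*Combined protocol and SAP*

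**What the plan says.** All references are to the combined protocol and SAP.

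- **Termination date (3.4.3).** "If subject is lost to follow-up, date of termination is the date of last documented contact with the subject". The section closes with "Study related procedures and documentation should end at the day of study termination for the respective subject". A separate bullet dates termination for a death at the date of death.
- **Tracing (3.4.2.5).** "At a minimum, the site should make two attempts to contact the subject by phone and one attempt by certified mail". These attempts come after the last contact, so they always postdate the termination date.
- **Adjudication (2.6 and 5.1.1).** The Clinical Events Committee (CEC) classifies the HF hospitalizations and cardiovascular deaths used in the primary endpoint and Secondary Endpoints 2 and 3. Its remit for hospitalizations is limited to the time a subject is enrolled in the sub-study. For deaths, "the CEC will adjudicate all deaths reported while participating in the MPP sub-study".
- **Missing data (2.6.1).** "The last observation carried forward (LOCF) principle will be utilized for the analysis of NYHA Classification and Patient Global Assessment". Nothing comparable is given for the two event components.
- **Population (2.6.2).** Intention-to-treat, "utilizing all available data from fully enrolled subjects".
- **Loss (2.5).** "Assuming a 10% loss to follow-up rate during the study for reasons unrelated to the study outcomes", 100 subjects are enrolled to give 90 evaluable.
- **Third-party information (6.2).** The investigator must make sure that relevant event information is available, including from family and other hospitals.

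**The concern.** Improved on the primary endpoint (2.1.1) needs a better NYHA class and also the absence of HF hospitalization and cardiovascular death. For a lost subject the plan supplies the first by carrying NYHA forward. It does not say how the second is established for the time after the last contact.

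Take a subject with improved NYHA at the 3-month MPP visit (day 90) who then misses the 6-month visit. The calls and certified mail fail, but while tracing, the site finds a record of an HF admission on day 120. Termination is dated day 90. The admission falls after the day on which documentation should end, and outside the period for which the CEC adjudicates hospitalizations. Followed literally, the subject stays Improved. Had the event counted, the subject would be Worsened.

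Subjects may be lost because they became sicker. The plan assumes that loss is unrelated to outcome, and these rules discourage collecting the information that would test this. Changing the NYHA imputation rule alone would not fill the gap, because the gap lies in the event components.

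**Working it through.** **1. The plan's own figure.** Inputs from 2.3.1.1: performance goal 3%, expected rate 10%, one-sided alpha 0.025, power 80%. With the exact binomial at n = 90, success needs at least 7 responders:

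- P(X ≥ 6 | 90, 0.03) = 0.0539 and P(X ≥ 7 | 90, 0.03) = 0.0188
- Power = P(X ≥ 7 | 90, 0.10) = 0.8075; at n = 89 it is 0.7983

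So 90 is reproduced, and 90 / 0.90 = 100 enrolled. The sample size is not in question.

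**2. The relevant denominator.** The concern arises only if lost subjects are analysed. Under 2.6.2 with LOCF that means n = 100, not 90:

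- P(X ≥ 7 | 100, 0.03) = 0.0312, exact 97.5% lower bound 2.86%: fail
- P(X ≥ 8 | 100, 0.03) = 0.0106, lower bound 3.52%: success

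The rule is at least 8 of 100 at 0.025 and also at the final level of 0.0224 (2.4). One subject can decide the result.

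**3. Who can be misclassified.**

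| Last NYHA against MPP enrollment | Primary endpoint if the event is not counted | Secondary Endpoint 3 if the event is not counted |
|---|---|---|
| Improved | Improved (false responder) | responder (false) |
| Unchanged, including a carried enrollment value | non-responder, no effect | responder (false) |
| Worsened | Worsened, no effect | non-responder, no effect |

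**4. Effect on the primary endpoint.** Let q be the share of the 10 lost subjects whose last NYHA was improved, and e the share of those with a qualifying event that is discovered but not counted. The documents give neither, so both are assumptions. Expected false responders = 10 × q × e. Type I error = P(A + B ≥ 8), with A ~ Bin(90, 0.03) and B ~ Bin(10, 0.03 + q·e):

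| q | e | False responders | Type I error |
|---|---|---|---|
| – | 0 | 0 | 0.0106 |
| 10% | 5% | 0.05 | 0.0116 |
| 10% | 10% | 0.1 | 0.0127 |
| 10% | 20% | 0.2 | 0.0151 |
| 20% | 20% | 0.4 | 0.0207 |
| 20% | 40% | 0.8 | 0.0358 |
| 30% | 40% | 1.2 | 0.0568 |

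At 0.50 expected false responders the error is 0.0240, and at 0.55 it is 0.0257, so nominal 0.025 is passed near 0.55. The final level of 0.0224 is reached near 0.45 (0.0223).

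**5. What e may include.** Events that nobody discovers are missed under any termination rule. Only discovered events are lost because of these sections, so e is smaller than the total event rate among lost subjects. The 40% one-year readmission-or-death figure in 1.2 concerns patients with HF-related hospitalizations. Subjects can enter this sub-study as Unchanged without one, so the figure is not used here.

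**The case against.** A reader might infer that lost subjects are simply carried forward as responders and that their later hospitalizations and deaths cannot count. The documents do not support that.

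- **Deaths.** Section 3.4.3 dates termination for a death at the date of death, and 3.4.2.3 sends deaths while enrolled to the CEC. A subject found during tracing to have died can exit as a death. What remains is narrower: no precedence is given between this rule and the lost-to-follow-up rule for a death learned of after exit.
- **No express bar.** The end-of-documentation sentence cannot be wholly literal. Death certificates, adjudication and the lost subject's own termination form all come after the termination date. Section 6.2 asks for information from other hospitals, and 2.6.2 uses all available data. Exclusion of a later admission is therefore an inference from 3.4.3 and 5.1.1, in tension with 6.2. This stands as a limit on the claim, but for a non-fatal HF admission no rule says which section governs.
- **Not every lost subject is a responder.** The primary endpoint needs an improved last NYHA. A subject lost before the 3-month visit would carry the enrollment value and be Unchanged.
- **Perhaps lost subjects are not analysed.** Section 2.5 removes them from the evaluable 90, and 2.6.1 explains that missing NYHA or PGA data "affects the number of subjects that can be included in the analysis", citing unanswered items rather than loss. Section 2.6.2 keeps every fully enrolled subject. The plan does not settle this.
- **Limited consequence.** Secondary Endpoint 3 has no hypothesis or performance goal, so a shift there changes no stated decision. The consent pages are not available, so whether record access after loss is already covered cannot be judged.

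**Conclusion.** The concern holds in a limited form. For a fully enrolled MPP subject declared lost, a non-fatal HF hospitalization after the last contact that comes to light during tracing is left outside collection and adjudication by the wording of 3.4.3 and 5.1.1. LOCF and intention-to-treat can still make that subject a responder, subject to the NYHA conditions above. For deaths, only the order of precedence after exit is open.

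The direction is certain: failing to count an event can only help the device. The size is small. At 0.1 to 0.2 expected false responders, type I error is about 0.013 to 0.015 with 100 analysed, below both 0.025 and 0.0224. A reader might infer that the primary test is materially inflated. That needs roughly half a false responder or more among 10 lost subjects, and the documents give no event rates that would establish it. The figures rest on 10 lost of 100, on all 100 being analysed, on a true rate of 3% in everyone, and on assumed q and e.

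It is worth correcting because a stated rule, followed literally, drops endpoint events that the site already has in hand, and the correction is cheap.

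**What to change.** Add to 3.4.3, with a matching sentence in 5.1.1:

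1. For fully enrolled MPP subjects, HF hospitalizations and deaths that occur up to the end of the 6-month window (180 + 30 = day 210 after MPP enrollment), and are identified from site or hospital records or from other parties, are reported, adjudicated by the CEC and counted in the composite, whatever the administrative termination date and within the limits of consent.
2. The end-of-documentation sentence and the lost-to-follow-up date do not exclude such events, including a death learned of after exit.

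The termination date itself need not change. It enters no endpoint formula, and moving it would only label unobserved time as participation.

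The cost is about two sentences and a record check for about 10 subjects, done alongside contact attempts that are already required. The downside is a slightly lower responder rate.

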3.4.2 Reasons for Study Termination

Once a subject is enrolled and successfully implanted, every effort should be made to continue to follow the subject in the clinical investigation. However, it is inevitable that some subjects will decline to participate further, change geographic location, or become non-compliant with the visit schedule.

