3.4.2.1 No implant attempt

If BIOTRONIK Ilivia 7 HF-T QP family CRT-D system or Acticor/Rivacor HF-T QP family CRT-D system and/or Sentus QP LV lead was not implanted, the subject is exited. The reason for study termination must be provided.

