5. STUDY OVERSIGHT

5.1 Clinical Events Committee

A Clinical Events Committee (CEC) consisting of at least 3 independent Electrophysiologists or Cardiologists (with CRT experience) will be established to review and adjudicate all MPP sub-study related events (Section 5.1). Protocol defined adverse events that are not MPP sub-study related will be included in the clinical report based on site-reported information.

The CEC will be blinded to the investigational site and subject identity, and to minimize bias members will not participate as investigators. The CEC will create a study specific charter defining the adverse event adjudication process, specifically detailing review guidelines along with appropriate response timelines.

The Clinical Events Committee is responsible for:

- Endpoint adjudication of adverse events meeting the criteria above
- Adjudication meetings, as needed, via telephone conference or face-to-face
- Regular reporting of adjudication results to the sponsor

The Clinical Events Committee will be supported by members of the sponsor in pre-selection of device complications from non-device related adverse events (e.g. broken leg, headache, cancer) and in organizational tasks.

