6.3 Reportable Adverse Events

6.3.1 Lead, System, and Procedure Related Event Examples

The following are examples of potential reportable adverse events and do not limit the required adverse event reporting as defined in Section 6.2.

Examples of reportable lead related events

- Ablation sequelae (such as lead dislodgement or damage during an ablation)
- Cardiac perforation occurring post implant
- Clinical lead failure
- High pacing threshold
- Extracardiac stimulation (e.g. phrenic nerve stimulation)
- Electrical lead failure
- Intermittent capture
- Lead abrasion
- Lead dislodgement or migration (not occurring during a procedure)
- Lead impedance out of range, high impedance
- Lead impedance out of range, low impedance
- Lead fracture or insulation damage
- Lead undersensing
- Lead-related thrombosis
- Loss of sensing
- No capture
- Mechanical lead failure
- Muscle or nerve stimulation
- Twiddler's syndrome
- Unsuccessful Sentus QP lead implant
- Lead repositioned, explanted, or replaced for any other reason

Examples of reportable system or pulse generator related events

- Device extrusion
- Device migration
- Inappropriate detection of arrhythmias
- Inappropriate therapy or shocks
- Inability to defibrillate or pace
- Myopotential sensing
- Pacemaker mediated tachycardia
- Premature battery depletion
- Pulse generator failure
- Shunting current or insulating myocardium during defibrillation with internal or external paddles
- Skin erosion
- Pulse generator repositioned, explanted, or replaced for any other reason

Examples of reportable major implant related events

- Air embolism
- Anesthetic complications
- Allergic reaction to components used at implant or during lead testing, or to components of the lead
- Arrhythmias associated with implant
- Arteriovenous fistula
- Body rejection phenomena
- Cardiac perforation with or without tamponade associated with lead implant
- Chronic nerve damage
- Coronary sinus dissection
- Damage to lead during a procedure
- Fluid accumulation
- Heart valve damage
- Major Hematoma
- Infection
- Keloid formation/fibrotic tissue formation
- Lead dislodgement of chronic leads that occurs during a procedure
- Loose set-screw
- Myocardial damage
- Non-healing pocket dehiscence or other wound healing disturbance
- Pericardial effusion
- Pericarditis
- Phlebitis
- Pleural effusion
- Pneumothorax associated with lead implant
- Pulmonary embolism associated with the implant procedure
- Respiratory arrest

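### A failed or partial implant is exited under the same rule as no attempt at all, so implant-procedure events after the decision date go unrecorded; no endpoint is affected

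*Combined protocol and SAP*

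**What the plan says.** The exit category is headed "3.4.2.1 No implant attempt", but its text tests something else: if the CRT-D system "and/or Sentus QP LV lead was not implanted, the subject is exited". Note 1 of section 3.3.3 (Implantation) applies the same test and exits the subject with a termination form.

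Section 3.4.3 fixes the date. Where the CRT-D and/or lead "was not implanted, the date of termination is the date of decision not to implant". It then adds: "Study related procedures and documentation should end at the day of study termination for the respective subject".

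The instruction to keep following subjects is limited to those with a successful implant: "Once a subject is enrolled and successfully implanted, every effort should be made to continue to follow the subject in the clinical investigation".

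Failed attempts are nevertheless foreseen. Section 6.3.1 gives "Unsuccessful Sentus QP lead implant" as an example of a reportable lead-related event, and item 3 of section 3.3.3 records whether the lead implant succeeded. On reporting, section 5.1 says: "Protocol defined adverse events that are not MPP sub-study related will be included in the clinical report based on site-reported information".

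**The concern.** A subject in whom an implant was tried and failed has undergone the procedure and carries its risk. Such a subject is treated like one who never had a procedure: observation stops when the decision not to implant is made. Several of the procedure events listed in section 6.3.1, such as infection, major hematoma, pericardial effusion or a pocket that does not heal, can first appear after the procedure day.

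The wording is also 'and/or'. A subject who leaves the procedure with the sponsor's CRT-D but without the Sentus QP lead is exited too, with a new generator in place. Section 6.2 asks for all events related or possibly related to the implanted system, yet this subject's later events fall outside collection.

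At stake is the completeness of the implant-procedure adverse event data, which section 2.1.5 names among the additional data of interest. The loss runs in one direction: events can be missed and none can be added.

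**Working it through.** The plan states no figure on this point, so there is nothing to reproduce. The check is a reading of the sections together, followed by a bound on scale.

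**1. Who falls under the rule.** Sections 3.3.3 (note 1), 3.4.2.1 and 3.4.3 all turn on the system not being implanted, and none turns on whether an attempt was made. The other categories in section 3.4.2 are withdrawal of consent, death, extraction before MPP enrollment, loss to follow-up and sub-study completion. None fits a failed attempt. The screen-failure definition in section 2.2 already takes some true no-attempt cases, namely subjects whose status changes before implant. Failed attempts therefore land in section 3.4.2.1 by default.

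**2. When observation ends.** Under section 3.4.3 it ends on the date of the decision not to implant. That term suits a subject with no attempt and is not defined for a failed one. If the attempt is abandoned for good, the date is the procedure day. If a repeat is planned and later dropped, the date falls after the first procedure.

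**3. Whether another route keeps collection open.**
- Section 6.2 follows ongoing events only until the earliest of the end of the subject's participation, the end of the study, or resolution. Exit therefore closes them.
- Section 3.4.2.3 asks for notice of deaths during the investigation. This could mean the whole study or the subject's own participation. Read with section 3.4.3, the second is more likely, so later deaths are probably lost.
- MedWatch reporting in section 8.1.2 is optional and is not study data collection.
- No section gives a safety window after a failed attempt.

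**4. What is still collected.** Section 3.3.3, item 10, records reportable events during the procedure, and the failed lead implant is itself reportable. The gap is limited to later-onset events, the outcomes of events ongoing at exit, and probably later deaths.

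**5. Which analyses are touched.** Sections 2.2 and 2.6.2 restrict the primary and secondary endpoints to fully enrolled MPP sub-study subjects. A subject exited without an implant never reaches that stage. Section 2.2 allows provisionally enrolled subjects into the additional data of interest, so only those data are affected.

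**6. Scale.** Subjects affected = N × f × q, where N is the number enrolled, f the share enrolled before implant, and q the share of those whose implant was attempted and failed. The documents give a maximum N of 1,754 (section 2.3) and neither f nor q. Setting f = 1 gives a ceiling for each assumed q:

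| Assumed q | 1,754 × q | Ceiling |
|---|---|---|
| 1% | 17.5 | about 18 |
| 5% | 87.7 | about 88 |
| 10% | 175.4 | about 175 |

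The true f is below 1 if any subjects enter under section 3.1.3 within 30 days after implant. Their study system is already in place, so they cannot be affected.

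**The case against.** The strongest case on the other side is that this is a wording matter in a secondary data set. The devices are market approved, implantation is a routine clinical decision, and the amendment exists to continue the MPP sub-study. Procedure events are not an endpoint. That holds and sets the severity. It does not remove the point, because the protocol still lists these events as study data and its exit rule cuts their collection short.

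A reader might infer more than the documents support:

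- **That every event from the day after the procedure is lost.** The cut-off is the decision date, which can fall later if a repeat attempt is planned.
- **That 1,754 gives an expected count.** It is a maximum, carried over from the sample size of the earlier post-approval cohort (section 2.3), and it includes subjects enrolled after implant. The number implanted under this text is not given.
- **That Appendix B supplies the missing event rate.** Its perioperative figures include events seen on the procedure day, and its categories do not match what the study counts. General infection is given as 1-7%, infection requiring reoperation as 0.6-2.0% and device-related infection as 0.03%. Appendix A counts an infection only if it needs intravenous antibiotics and/or system removal. Nothing gives the share of events that appear later.
- **That a reported rate is biased by a known amount.** No procedure event rate with a fixed denominator is specified. Section 2.2 says only that provisionally enrolled subjects may be included. Under-recording follows from the text, but its effect on any particular rate does not.
- **That all successfully implanted subjects are observed for about 6 months.** Subjects explanted before MPP enrollment without an eligible replacement also exit on the revision date (sections 3.4.2.4 and 3.4.3).

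**Conclusion.** The point holds in a limited form. Sections 3.3.3 (note 1), 3.4.2.1 and 3.4.3 do not separate subjects with no attempt from those with an attempt but no complete implant. Followed as written, they end collection for the second group on a date that may be the procedure day, and section 6.2 closes any events still open. Implant-procedure adverse events are under-recorded as a result. The size cannot be derived; the ceilings of about 18 to 175 subjects rest on assumed failure rates of 1% to 10% and on everyone enrolling before implant. No count of missed events is supportable. The conclusion on later deaths depends on reading section 3.4.2.3 as the subject's own participation. No primary or secondary endpoint is affected. This is a cheap improvement.

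**What to change.** Reconcile sections 3.3.3 (note 1), 3.4.2.1, 3.4.3, 6.2 and 6.3.1 together. Changing only the two termination sections would leave the Implantation note and the event follow-up rule in conflict with them.

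- Limit the exit on the decision date to subjects with no implant attempt, as the heading of section 3.4.2.1 already implies.
- Add a category for subjects with an attempt but no complete implant, including a CRT-D placed without the Sentus QP lead. Set their exit at the end of a stated data-collection window, for example 30 days after the last attempt. The 30 days is a proposal; the documents give no basis for a particular length.
- Within that window, collect procedure- and system-related adverse events, the outcomes of ongoing events, and vital status by record check or telephone.
- Report procedure events over all attempted implants among subjects enrolled before implant. Subjects enrolled afterwards enter only if the implant succeeded, so adding them would select on success.

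The cost is a few sentences and one remote check per failed attempt. Procedure event rates may look slightly less favourable.
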